#### Objective 2:

Treatment duration will be reported for the first prescribed treatment. Cumulative dose will be calculated considering all treatments containing NOMAC or CMA recorded during the study period. For the pre- and postintervention comparison, cumulative dose and treatment will be calculated for all treatments initiated over one year before (or six months, if insufficient follow-up data is available) and after the intervention.

Exposures of interest (NOMAC vs. CMA) will be assessed separately. Results will be reported overall and stratified by study period and indication at first use.

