## 8.4 Follow-up

For the population-level DUS (objective 1), study participants in the denominator population will start contributing person time on the latest of the following: 1) study start date (1st January 2010, or as defined according to the database), 2) date on which they turn 10 years old, 3) date at which they have a year of prior history recorded. Participants will stop contributing person time at the earliest date of the following: 1) end of available data in each of the data sources, 2) date at which their observation period ends (e.g. loss to follow-up, death).

For the patient-level DUS (objective 2 to 5), participants will be followed up from the day of incident prescription of medication (index date), until the earliest end of data availability, date at which their observation period ends (e.g. loss to follow-up, death), or 180 days after ending treatment (objective 5). For objective 2, 4 and 5, index date will be defined as the date of the first-ever prescription of NOMAC or CMA. For objective 3, this will be defined as the date of the first-ever prescription of any of the 6 drug classes of interest (see "8.6.2 Outcomes").

For objective 4, line of treatment will be assessed retrospectively by looking at prior records of alternative treatments, from the date of initiation of treatment with products containing NOMAC or CMA to start of the study period (1st January 2010, or as defined according to the database).

For objective 6, follow-up will be the same as that for objective 1.

Information on the operational definition of index date is described in **Table 4**. Please note that, for objectives 1 and 6, each drug class of interest will be assessed separately, with the washout window specific to the drug class being studied (e.g., when studying NOMAC, the washout window will be applied with respect to this substance only). For objective 3, the washout will be applied to all the drug classes of interest combined.

Authors: [name], [name], [name], [name], [name]

Version: V4.0

**Dissemination level:** Public

Table 4. Operational definition of time 0 (index date) and other primary time anchors.

Study population names	Time Anchor Description (e.g. time 0) 	Number of entries 	Type of entry	Washout window	Care Setting 	Code Type 	Incident with respect to

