General population (objective 1 and 6)	Study entry date	Multiple entry	Incident , prevale nt	[-365, -1]	IP, OP	N/A	Outcome drug class (assessed separately)
Patients with prior history of meningioma (objective 1, subgroup analysis)	Date of diagnosis	Single entry	Incident	[-Inf, 0]	IP, OP	SNOME D	Meningiom a
New users of NOMAC (objective 2, 4 and 5)	Date of prescription	Single entry	Incident	[-Inf, -1]	IP, OP	RxNorm	NOMAC
New users of CMA (objective 2, 4 and 5)	Date of prescription	Single entry	Incident	[-Inf, -1]	IP, OP	RxNorm	СМА
New users of drug classes or progestogens of interest (objective 3)	Date of prescription	Single entry	Incident	[-Inf, -1]	IP, OP	RxNorm , SNOME D	Drug classes of interest (any)

¹ Study entry date (objective 1 and 6) will be defined as the latest of the following: 1) study start date (1st January 2010, or as defined according to the database), 2) date on which they turn 10 years old, 3) date at which they have a year of prior history recorded.

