## 8.7 Study size

The expected number of patients exposed to NOMAC or CMA is expected to be roughly between 1,900 in NAJS and 16,800 in IQVIA DA Germany and between 2,4004 in IQVIA LPD Belgium and 173,900 in IQVIA

<sup>2Specify whether a diagnosis code is required to be in the primary position (main reason for encounter)

<sup>3 These will include: meningioma, obesity, diabetes mellitus, type 2 neurofibromatosis, asthma, autoimmune diseases, epilepsy, uterine fibroids, menopause/perimenopause, primary ovarian insufficiency, endometriosis, polycystic ovarian syndrome, menstrual disorders, neoplasm of the endometrium, neoplasm of the brain, neoplasm of the breast, cancer (any malignancy), hyperlipidaemia, hypertensive disorder, osteoporosis, venous thromboembolism.

<sup>4 These will include: progestogen and oestrogen combination products not containing NOMAC or CMA, progestogens that are pregnadien derivates not containing NOMAC or CMA, progestogen and oestrogen combination products not containing NOMAC or CMA, NOMAC, CMA, medroxyprogesterone, antidepressants, metformin, bisphosphonates, clonidine, gonadotropin releasing hormone antagonists and anti-androgens.

Authors: [name], [name], [name], [name], [name]

Version: V4.0

**Dissemination level:** Public

DA Germany, respectively. These counts were provided as part of the feasibility assessment and correspond to the entire source data, without restriction on age, sex or study period.

No specific sample size calculations have been performed. Given that meningioma is a rare tumour, we expect to have limited sample size in Objective 1, when restricting the population to individuals with prior history of meningioma. For Objective 3, 4 and 5, we expect an adequately large sample size to estimate Standardised Mean Differences (SMD) accurately. For Objective 2, this might be more limited as we will only consider users initiating treatment within a period of 6 to 12 months.

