## Objective 2:

Treatment duration will be reported for the first prescribed treatment. Duration will be derived from the start and end of the prescription.

Cumulative dose will be calculated considering all treatments containing NOMAC or CMA recorded during the study period. If two eras with different doses are separated by less than 30 days, the time between the two eras will be considered as exposed by the first era (Figure 1, first row). If two eras start at the same date, the overlapping period will be considered exposed by both.

[figure not shown]

Figure 1. Gap era joint mode

Cumulative dose and treatment duration will be calculated for all treatments initiated during the study period and occurring over one year before and after the intervention to compare time periods of equal duration. The pre-intervention period for comparison will span from October 2021 to September 2022,

Authors: [name], [name], [name], [name], [name]

Version: V4.0

Dissemination level: Public

the year prior the request for PRAC to review current evidence on NOMAC and CMA. The post-intervention period for comparison will span from February 2023 to January 2024. For databases with less available data (see Table 3) we will limit the comparison to 6 months (post-intervention: February to July 2023; pre-intervention: February to July 2022). Time periods for comparison will cover the same calendar months in case seasonality is detected.

NOMAC and CMA will be assessed separately. Results will be reported overall and stratified by study period (pre- vs. postintervention) and indication at first use (non-HRT vs. HRT).

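### Objective 2 fixes the unit of treatment duration in two conflicting ways: the first prescribed treatment, and, in the pre/post rule, all treatments initiated in the window

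*Protocol*

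**What the plan says.** Section 8.8, Objective 2, opens with a per-woman unit for duration: "Treatment duration will be reported for the first prescribed treatment". It sets this apart from dose: "Cumulative dose will be calculated considering all treatments containing NOMAC or CMA recorded during the study period".

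The pre/post rule, a few lines later, puts the two together: "Cumulative dose and treatment duration will be calculated for all treatments initiated during the study period", with the window added as "occurring over one year before and after the intervention to compare time periods of equal duration". The abstract has a similar pair. It repeats the first-treatment sentence and then says "cumulative dose and treatment will be calculated for all treatments initiated over one year before"; the word 'duration' is missing there, so the abstract is weaker evidence on this point than section 8.8.

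The cohort is one entry per woman. Section 8.4 states "For objective 2, 4 and 5, index date will be defined as the date of the first-ever prescription of NOMAC or CMA", and the NOMAC row of Table 4 reads "Date of prescription Single entry Incident [-Inf, -1] IP, OP RxNorm NOMAC". On sample size, section 8.7 says of Objective 2 that "we will only consider users initiating treatment within a period of 6 to 12 months".

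The summary measure is the median with range and interquartile range (Table 1). The pre/post contrast is the SMD (section 8.8, Objectives 2-5). Table 11 carries the hypothesis that duration and cumulative dose will be lower after the restrictions.

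**The concern.** The pre/post contrast is the result that bears on the Objective 2 hypothesis, and its unit is stated in two ways that give different numbers.

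Under the first sentence, each woman contributes one duration. Under the literal pre/post rule, each course contributes one. A woman with three courses then counts three times. A woman first treated years earlier belongs to the cohort, and a new course that she starts inside the window would also count. If the share or the length of repeat courses differs between periods, the median and SMD of duration shift even when first treatments are unchanged.

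Repeat courses are not hypothetical in this protocol: restarting the same treatment is one of the outcomes described under Objective 5. Table 11 also expects more discontinuations and switches after the restrictions, so a change in course mix between periods is plausible.

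**Working it through.** The protocol gives no course lengths, repeat rates or sample size for Objective 2, so there is no figure of its own to reproduce. All inputs below are assumptions, chosen to show how far the unit alone can move the result. Throughout, SMD = (post mean - pre mean) / sqrt((pre variance + post variance) / 2).

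**Two-group arithmetic.** A share w of women have one 180-day course (SD 60). The rest have k courses of 30 days each (SD 10).

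- First-treatment mean = 180w + 30(1 - w), which does not depend on k, so the SMD is 0.
- All-courses mean = [180w + 30k(1 - w)] / [w + k(1 - w)].
- Share of courses that are long: p = w / [w + k(1 - w)].
- Variance over courses = 60²p + 10²(1 - p) + 150²p(1 - p).

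With w = 0.7, the first-treatment mean is 126 + 9 = 135 days in both periods. For all courses:

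- k = 4 before: (126 + 36)/1.9 = 85.3 days, p = 37%.
- k = 2 after: (126 + 18)/1.3 = 110.8 days, p = 54%.
- Change +30%. Variances about 6,625 and 7,576, so SMD = 25.5/84.3 = +0.30.

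With w = 0.85 and k falling from 3 to 1.5: 166.5/1.3 = 128.1 to 159.75/1.075 = 148.6 days, +16%, SMD about +0.24.

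With w = 0.7 and k falling from 1.5 to 1: 139.5/1.15 = 121.3 to 135 days, +11%. Variances about 7,590 and 7,275, so SMD = 13.7/86.2 = +0.16.

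**Simulation with the repeat length varied.** There were 400,000 women per period, starting uniformly over 365 days. First courses were exponential with mean 120 days in both periods. A repeat followed with probability 0.6 before and 0.1 after, starting 30 days plus an exponential delay (mean 30) after the first course ended. This puts a repeat inside the window for 32% and 5% of women. SMDs, post minus pre:

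| Mean repeat course (days) | All courses, no cut-off | All courses, cut off at window end | Sum per woman, no cut-off |
|---|---|---|---|
| 40 | +0.14 | +0.14 | -0.09 |
| 80 | +0.06 | +0.08 | -0.18 |
| 120 | 0.00 | +0.04 | -0.25 |
| 180 | -0.09 | 0.00 | -0.33 |

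First treatment only: between -0.004 and +0.004 in every scenario, as it should be. In the 40-day row without cut-off, the all-courses median moves from 62.7 to 78.8 days.

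So the same prescribing can appear as longer, unchanged or shorter treatment, depending on the unit.

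**The case against.** The strongest reply is that the rest of the protocol largely settles the unit. Section 8.4, Table 4 and Table 6 give one entry per woman at first-ever use and exclude prior users. Table 10 describes the SMD as a comparison of new users before and after. Section 8.7 speaks of users starting treatment. Objective 2 is stratified by the indication when the drug was first used, which is a per-woman value. Section 8.6.3 speaks of treatments started in the transition period for Objectives 1 to 5, including objectives where each woman enters once. Where prevalent users are admitted, under Objective 5, the protocol says so.

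This stands as evidence of the probable intent, and it is why the fix takes that direction. It does not remove the conflict. The cohort rule fixes which women enter, not which of their courses count, and the same cohort uses all courses for cumulative dose. A programmer who follows the pre/post sentence literally would count courses.

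The two-group figures are also favourable to a large effect. On the data locks in Table 3 (30-09-2023, 31-12-2023 and 17-11-2023), no database reaches January 2024. The six-month windows would then apply to all three, which leaves less room for repeats. In NAJS, starts less than 90 days apart are merged (section 11). This stands: +0.30 is the upper end of an illustration, not an estimate.

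**Conclusion.** The conflict is in the text, and it affects the pre/post duration contrast. Read literally, the pre/post rule gives a course-weighted comparison that can move through course mix alone, with an illustrative SMD of about -0.1 to +0.3. Those values rest wholly on assumed course lengths and repeat rates.

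Three stronger readings are tempting, and the documents do not support them.

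- A reader might infer that fewer repeat courses after the measures would make treatment look longer. That needs repeat courses that are shorter than first ones or cut off by the window. With longer, uncut repeats the sign reverses.
- A reader might take fewer repeat courses to be an aim of the measures. Section 6 names lowest effective dose, shortest duration, no first-line use, and contraindication, monitoring and discontinuation in relation to meningioma. It does not name repeat courses.
- A reader might object that several courses per woman are not independent. Dependence does not bias a descriptive SMD; the weighting is what matters.

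The point deserves correction before analysis, because the unit would otherwise be chosen when results are in view. The rest of the study is not affected.

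**What to change.** In section 8.8 (Objective 2) and in the abstract:

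- Define the pre/post duration comparison as the duration of the first treatment of each woman whose first-ever prescription of the drug falls in the window, one value per woman. This agrees with section 8.4, Table 4, section 8.7 and Table 10.
- Define cumulative dose as one total per woman over the same bounded length of follow-up in both periods, for example a fixed time from index, or up to the end of each equal-length window. It should not run open-ended from index. With the NAJS lock of 17-11-2023, women starting in February-July 2022 could accumulate dose for about 15.5 to 21.5 months, and those starting in February-July 2023 for about 3.5 to 9.5 months. Dose would then look lower after the restrictions with no change in prescribing. A fixed time from index must be short enough for the last entrants before the lock.
- State whether the same bound applies to first treatments still running at that point.
- Label any all-courses result, or the number of courses per woman, as separate and descriptive.

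The cost is wording only, with no new data. The downside is that repeat courses no longer add observations to the duration comparison.

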## Covariates for stratification:

- Age group: 10-17, 18-34, 35-49, 50-64, +65 years (Objective 1)
- Dose: High- vs. low- dose, for NOMAC and CMA only (Objective 1,4,6)
- Indication: HRT (hormonal replacement therapy) vs. non-HRT, with age as a proxy (Objective 1,2,4,6)
- WHO ATC 5th level code: For NOMAC and CMA only (Objective 1 and 5).
- Study period: Pre- vs. Postintervention (Objective 1 to 5).

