In July 2022, PRAC issued further recommendations for both NOMAC and CMA. PRAC recommended to update the summary of product characteristics for products containing NOMAC or CMA to inform of the risk of meningioma. PRAC recommended that medicines containing high-dose chlormadinone (5 – 10 mg) or high-dose NOMAC (3.75 – 5 mg) should be used at the lowest effective dose and for the shortest duration possible. These medications should only be used when other interventions are not appropriate and should no longer be considered for first-line treatment. Similar to what was already established for NOMAC, treatment with products containing NOMAC or CMA was contraindicated in patients with current or prior history of meningioma. PRAC also recommended monitoring patients for symptoms, and permanently discontinuing treatment if the patients develop meningioma. (9) Measures recommended by PRAC were endorsed by the Committee for Medicinal Products for Human Use (CHMP) and the European Commission issued final legally binding decisions applicable in all the European Union (EU) Member States, between 28th of October and 28th November 2022.(10) Following this decision, a direct healthcare professional communication (DHPC) was sent to prescribers (8th November 2022)(11) and Marketing Authorisation Holders (MAH) had one month to implement changes (28th December 2022). Dates for national-level interventions varied, especially in the case of France, where additional interventions were put in place between 2018 and 2021.

The overall aim of the study is to describe how prescribing of NOMAC and CMA has changed following the introduction of risk minimisation measures (RMM) in November 2022. To contextualise findings, it is also of interest to study changes in prescribing of other relevant drug classes, including progestogen and oestrogen combination products and progestogens that are pregnadien derivatives, and to study the impact of prior EU-level restrictions in trends of NOMAC prescribing.

D2 C	2 000	Charles	Donate and
P3-C.	3-UU6	Stuav	Protocol

Version: V4.0

**Dissemination level:** Public

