#### Objective 4:

For each participant initiating treatment with NOMAC or CMA, we will retrospectively assess the occurrence of records indicating the use of other drug classes of interest not containing NOMAC or CMA. This assessment will be performed from the day before index date to the earliest of the start of the study period or the start of the observation period for each patient. We will describe the order in which treatments of interest were prescribed, as first vs. non-first treatments. NOMAC and CMA will be assessed separately.

NOMAC and CMA will be assessed separately. Results will be reported overall and stratified by study period (pre- vs. postintervention), dose (high- vs. low-dose products), and indication (non-HRT vs. HRT). Dose and indication will be assessed at index date (i.e. date of treatment initiation with NOMAC or CMA). Please see "11. Limitations" for more information.

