#### A. Primary analysis

Hypothesis:	Objective 1: Not applicable, descriptive analysis.
	Objective 2: Cumulative dose and duration of treatments with NOMAC or CMA will be lower after the implementation of restrictions.
	Objective 3: The number of new users of NOMAC or CMA with prior history of meningioma will be reduced after the implementation of restrictions.
	Objective 4: The number of users initiating NOMAC or CMA as first-line treatment will be reduced after the implementation of restrictions.
	Objective 5: The number of discontinuations and switches from NOMAC or CMA to other drug classes will increase after the implementation of restrictions.
	Objective 6: The incidence of NOMAC or CMA will be reduced after the implementation of restrictions, especially for high-dose products. This reduction will not be observed for other drug classes of interest.
Exposure contrast:	Objective 1: Not applicable, descriptive analysis.
	Objective 2: Pre-intervention (1-year period) vs. Post-intervention (1-year period)
	Objective 3 to 6: Pre-intervention vs. Post-intervention
Outcome:	Objective 1: Incidence rates and prevalence of drug classes of interest
	Objective 2: Cumulative dose and treatment duration of NOMAC or CMA.

Authors: [name], [name], [name], [name], [name]

Version: V4.0

Dissemination level: Public

	Objective 3: Number and characteristics of users of drug classes of interest.
	Objective 4: Line of treatment when initiating NOMAC or CMA.
	Objective 5: Diagnosis with meningioma during treatment. Discontinuations and switches
	from treatments with NOMAC or CMA to others.
	Objective 6: Incidence rates of NOMAC or CMA.
	Drug classes of interest, NOMAC and CMA will be assessed separately.
Analytic software:	R
Model(s):	Objective 1: Not applicable, descriptive analysis.
	Objective 2 to 5: Standardised mean differences.
	Objective 6: Segmented regression (Poisson models).
Confounding adjustment method	
	Stratification.
Missing data methods	
	The absence of a record for a condition or medication will be considered as the absence of the disease or use of the medication.
Subgroup Analyses	
	Objective 1: Age groups, indication, study period. For NOMAC or CMA only: dose, WHO ATC 5 th level (if counts allow). A subgroup analysis will be performed restricting the study population to individuals with a prior history of meningioma.
	Objective 2: Study population, indication, study period.
	Objective 3: Study period.

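### Objective 2 has no high/low-dose stratum, so it cannot show whether high-dose use, the target of the dose and duration restriction, became shorter or lower

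*Protocol*

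**What the plan says.** **The restriction.** Section 6 states that high-dose CMA (5-10 mg) and "high-dose NOMAC (3.75 – 5 mg) should be used at the lowest effective dose and for the shortest duration possible". The measures covering every strength concern meningioma itself: "treatment with products containing NOMAC or CMA was contraindicated in patients with current or prior history of meningioma", together with symptom monitoring and stopping treatment if a meningioma develops. The abstract's background draws the same line.

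**The Objective 2 hypothesis.** Tables 1 and 11 carry no dose qualifier: "Cumulative dose and duration of treatments with NOMAC or CMA will be lower after the implementation of restrictions".

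**The Objective 2 strata.** Section 8.8 says: "Results will be reported overall and stratified by study period (pre- vs. postintervention) and indication at first use (non-HRT vs. HRT"). Table 11 gives "Objective 2: Study population, indication, study period". The abstract and the Objective 2 list in section 8.6.3 agree. The abstract's list of stratification covariates has "Dose: High- vs. low- dose, for NOMAC and CMA only (Objective 1,4,6"), so Objective 2 is left out.

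**The closest comparator.** Objective 4 is also a patient-level analysis of new NOMAC or CMA users. It is split by "dose (high- vs. low-dose products), and indication (non-HRT vs. HRT). Dose and indication will be assessed at index date".

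**The concern.** The one measure aimed at dose and duration applies to high-dose products. The one objective that measures dose and duration combines them with low-dose products, which section 6 says are also used for contraception. The omission is consistent across the abstract, sections 8.6.3 and 8.8 and Table 11, so it is a fixed choice and not a detail left for later. No reason is given, and section 11 does not list it as a limitation.

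Two things are at stake. A real shortening among high-dose users may be too diluted to see. A fall in pooled cumulative dose may reflect shorter or lower use of high-dose products, or only fewer women starting them, and Objective 2 as planned could not say which.

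**Working it through.** **Step 1. Is dose level available from another Objective 2 stratum?** NOMAC and CMA are analysed separately, which does not separate strengths. Indication is a proxy based on age 50. Section 6 lists gynaecological and menstrual disorders as indications alongside lower-dose contraception, so women aged 10-49 can be on either dose level. The proxy may separate some use but is not built to separate dose. Objective 4 uses both indication and dose, so the protocol does not treat one as a substitute for the other.

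**Step 2. Is duration or cumulative dose reported by dose level elsewhere?** No.
- Objectives 1 and 6 report incidence by dose level (Objective 1 also prevalence).
- Objective 3 counts high- and low-dose initiators.
- Objective 4 reports line of treatment by dose level.
- Objective 5 concerns switching, discontinuation and meningioma.

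**Step 3. Does the protocol expect the mix to change?** Yes. The Objective 6 hypothesis expects incidence to fall, most of all for high-dose products.

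**Step 4. Size.** The protocol states no expected difference for Objective 2, so there is no figure to reproduce. It also does not give the high-dose share (h), the durations, their spread or the low-dose strengths. Everything below is assumed and shown over a range.

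Formulas: pooled mean = h × high-dose mean + (1 − h) × low-dose mean. Standardised mean difference (SMD) = (post mean − pre mean) / √((pre variance + post variance)/2), using the mixture variance.

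*(a) Dilution, stable mix, no change in low-dose users.* With equal mean durations, the overall percentage change is h × 30%. For the SMD, both strata start with the same mean and SD, and the true high-dose SMD is −0.30.

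| High-dose share | 30% shortening appears as | Pooled SMD |
|---|---|---|
| 5% | 1.5% | −0.015 |
| 10% | 3% | −0.03 |
| 50% | 15% | −0.15 |

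*(b) Mix shift alone, no change within either dose level.* CMA, 84 days each, low dose assumed 2 mg (2 × 84 = 168 mg), high-dose share falling from 30% to 10%:
- At 5 mg (5 × 84 = 420 mg): before, 0.3 × 420 + 0.7 × 168 = 243.6 mg; after, 0.1 × 420 + 0.9 × 168 = 193.2 mg. The fall is 50.4/243.6 = 21%.
- At 10 mg (10 × 84 = 840 mg): before, 0.3 × 840 + 0.7 × 168 = 369.6 mg; after, 0.1 × 840 + 0.9 × 168 = 235.2 mg. The fall is 134.4/369.6 = 36%.

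For NOMAC (assumed low dose 2.5 mg, 90 days each, share falling from 50% to 25%), the fall is 10% at 3.75 mg and 17% at 5 mg.

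*(c) Both together, for duration.* High-dose mean falls from 60 to 48 days (coefficient of variation 0.7, SMD −0.32). Low-dose mean stays at 120 days. The share falls from 50% to 25%. Before: 0.5 × 60 + 0.5 × 120 = 90 days. After: 0.25 × 48 + 0.75 × 120 = 102 days. The pooled SMD is +0.16, the opposite sign. If low-dose duration is also 60 days, the pooled SMD is −0.07, so a reversal needs low-dose treatment to last longer.

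**Step 5. With a dose stratum.** In (a) and (c) the high-dose stratum shows its own SMD (−0.30 and −0.32). In (b) each stratum correctly shows no change.

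**The case against.** **A move from high- to low-dose products is partly what the measures intend.** Section 6 says high-dose products should be kept for cases where other interventions are not appropriate. The hypothesis concerns all NOMAC or CMA treatments, and the pooled contrast addresses it. This stands. A reader might infer that the comparison is confounded by product mix, but the documents do not support that label: the mix lies on the pathway of the measure, and the pooled figure is a valid overall description.

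**A mix shift would be visible.** Objective 3 counts high- and low-dose initiators by period, Objectives 1 and 6 split incidence by dose, and Table 10 lists the distribution of initial dose or strength. This also stands. Those counts reveal a shift, but they do not show duration or cumulative dose within a dose level.

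**A high-dose stratum has its own problems.** Women still started on high dose after the restriction may differ from those started before it. Cumulative dose counts all later treatments and allows eras at different doses, so dose at index does not isolate high-dose exposure. This rules out letting the high-dose stratum alone decide the hypothesis, since that would also drop the intended shift from view. It does not rule out reporting the stratum. The problem is smaller for duration, which is taken from the first prescribed treatment.

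**The sizes are assumed, and the main summary is a median.** True. Table 1 names the median with range and quartiles, and the arithmetic above on means bears directly only on the SMD.

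**Cells will be small.** Section 8.7 already expects limited numbers for Objective 2. This is a cost, not a reason to omit the stratum.

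**Conclusion.** The point holds as a gap in what Objective 2 can answer. As written, the protocol cannot show whether high-dose CMA or NOMAC came to be used for shorter periods or at lower cumulative dose, although that is what this measure asks for. It should be corrected, but it does not invalidate the planned overall comparison.

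That conclusion rests on the text alone. The size of the problem does not: it depends on the high-dose share in each database, how far that share moves, and how durations differ between dose levels, none of which the protocol gives. Under the assumptions shown, a 30% shortening shrinks to between 1.5% and 15%, and a mix shift alone moves mean CMA cumulative dose by about 21% to 36%. These are illustrations, not predictions.

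**What to change.** Add dose at index date (high versus low, as defined in section 8.6.3 and timed as in Objective 4) to the Objective 2 stratifiers in the abstract (covariate list and Objective 2 paragraph), section 8.6.3, section 8.8 and Table 11. Extend the dose row of Table 9, now labelled for the Objective 1 and 6 population only, to the new-user population of Objective 2.

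Report the high-dose before/after comparison as a key result beside the overall one, not in its place, with the low-dose stratum as contrast. State that it is to be read with the Objective 3 counts of high- and low-dose initiators, because the women started on high dose may differ between periods.

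The cost is one already defined covariate in one analysis. The downside is sparse cells, mainly NOMAC in NAJS (1.9k) and CMA in IQVIA LPD Belgium (2.4k). Both are whole-database counts before any restriction by age, sex or period. The existing rule of showing counts below 5 as <5 covers reporting, and the protocol's if-counts-allow wording could be reused.
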